### Central Pain Sensitivity May Predict Differential Response to PA for Low Back Pain

To date it has been challenging to understand why some individuals with cLBP respond favorably to evidence based interventions, such as PA, and others do not. One factor that may underlie this differential treatment response is central pain sensitivity. Findings from cLBP studies suggest that some patients have an augmented pain sensitivity, in which the pain experience results from or is exacerbated by abnormal pain processing rather than damaged or inflamed peripheral structures. As such, pain sensitivity may prove useful in understanding an ongoing refractory pain-process and particularly why some patients do not respond to a PA intervention alone. There is evidence that psychosocial characteristics such as pain catastrophizing and depression contribute to pain sensitization, and CBT-P can improve these psychological processes and outcomes. Therefore older adults with cLBP who have higher baseline pain sensitivity may respond better when PA is combined with CBT-P versus a PA program alone. However, this has not been investigated, and this pilot study will be an important step in this area of research.

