The baseline visit will include administration of consent, baseline questionnaires and functional assessments, and an examination by a physical therapist ([name]). During the physical therapist exam a Well Straight Leg Raise physical examination test will be used to determine the presence of ongoing sciatica, which may be exacerbated with physical activity. This test is conducted with the participant in supine position and the examiner supporting the non-involved leg. The examiner then raises the leg. A positive test is indicated if the participant reports concordant leg pain. This test is commonly used in clinical practice and is highly specific for sciatica (specificity=97%). Results of the physical therapist examination will be used to determine physical appropriateness for participation in the home-based PA program, based on the clinical expertise of the physical therapist and the criteria described below. If the physical therapist determines that the patient is not appropriate for participation in a home exercise program, the patient's primary care provider will be notified via response to the consult if the patient was referred by the provider, and that provider may refer the patient for more supervised physical therapy. All other non-qualified patients will have a progress note entered into CPRS stating that they may benefit from supervised physical therapy. During the baseline visit the participants will also receive a packet with several self-administered measures to fill out either at that time, or they can complete the questionnaires at home and then mail them back to the study team using a pre-addressed stamped envelope. We will monitor the return of these items and may need to do telephone follow-up calls to ensure that all measures are returned.

**Randomization:** Following the completion of all baseline assessments and the physical therapist examination, participants will be randomly assigned to one of the two intervention arms or to the wait list control group via an envelope selection procedure or by use of a randomization table programmed into the study tracking database. Randomization will be stratified by Central Sensitization Inventory (CSI) score (described below under Measures of Central Pain Sensitization), categorized by >40 vs. ≤40; this to ensure individuals with high vs. low pain sensitivity will be equally distributed across study groups.

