The principal investigator, project coordinator, or physical therapist will select an envelope from one of two batches. One batch of envelopes will be for participants who have a CSI score of >40. The other batch of envelopes will be for those with CSI ≤40. Following randomization, participants assigned to the PA or PA + CBT-P intervention will receive their first intervention visit from the physical therapist, unless they need to complete this at another time for scheduling reasons.

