**Inclusion / Exclusion Criteria:** Based on previous studies, we will **include participants who:**

- 1) Self-report having had lower back pain on most days for greater than three months.
- 3) Can complete a 10 second semi-tandem stand and walk 8' in 6.0 seconds.
- 4) Report they are not satisfied with their current state of functional ability, based on reporting "dissatisfied" with at least one aspect of physical function on the Satisfaction with Physical Function Scale.
- 5) Can safely participate in the intervention based upon the physical therapist baseline examination and clinical expertise.

Veterans will be **excluded if they have:**

- 1) acute unilateral or bilateral sciatica (based on Physical Therapist exam at baseline); isolated coccyx pain (based on self-report at screener);
- 2) dementia or other significant cognitive impairment;
- 3) movement or motor neuron disorders (e.g., Parkinson's Disease, Multiple Sclerosis, Amyotrophic Lateral Sclerosis);
- 4) rheumatoid arthritis, fibromyalgia, or other systemic rheumatic disease;

- 5) hospitalization for a stroke, myocardial infarction, heart failure, or coronary artery revascularization in the past 3 months;
- 6) significant hearing impairment (must be able to talk on the telephone);
- 7) psychosis or current, uncontrolled substance abuse disorder;
- 8) legally blind;
- 9) any other health conditions determined by the study team to be contraindications to performing mild to moderate home exercises.

Based on our prior and ongoing studies at the Durham VAMC that have similar recruitment and procedural methods, we are confident we can enroll n=60 older veterans with cLBP within the proposed recruitment period for this study. Study participants excluded after consent due to the presence of sciatica or other functional limitations or health problems as determined by the physical therapist at baseline will not be randomized and thus not included in our total enrollment goal, i.e. we plan to consent enough participants such that a total of n=60 are eligible to participate, having met the eligibility criteria assessed following consent.

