**Analyses**: We will compare outcomes across study groups with analysis of covariance (ANCOVA) models (or non-parametric alternatives such as the Kruskal-Wallis test, when indicated), controlling for baseline values. Since this is a pilot study with small sample size, even clinically relevant differences may not be reflected as statistically significant differences (e.g. p<0.05). Therefore we will focus on effect sizes for the two intervention groups and evaluation of whether between-group difference reflects a threshold of clinical relevance. These data, along with means and standard deviations of baseline scores, correlations between baseline and follow-up scores, and attrition rate will also be used to calculate the appropriate sample size for a larger clinical trial. To address Aim 3, we will first plot baseline PPT and CSI values vs. changes in outcomes for each intervention group; we will also calculate correlations for these same associations. This will allow us to evaluate whether associations between baseline pain sensitivity measures and changes in outcomes may differ between the two intervention groups. Based on our previous experience with analyzing PPT data, we will also dichotomize these baseline scores at a <4kg vs. >=4kg to represent low and high pain sensitivity. We will then add an interaction term to our ANCOVA models (study group \* dichotomous PPT variable) to evaluate whether intervention effects vary by this indicator. If a significant interaction term is found, we will stratify the sample by this variable and explore the nature of the interaction. A similar analysis will be conducted with the established cutpoint on CSI scale or 40 out of 100.

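### Randomisation is stratified by CSI, but the Aim 2 ANCOVA leaves the stratum out; if CSI is prognostic, some precision is lost, at no risk of bias

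*Combined protocol and SAP*

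**What the plan says.** The Randomization section states: "Randomization will be stratified by Central Sensitization Inventory (CSI) score", with a cut at 40. The reason given is "this to ensure individuals with high vs. low pain sensitivity will be equally distributed across study groups". For the envelope method, "One batch of envelopes will be for participants who have a CSI score of >40", and a second batch serves those at 40 or below. A randomisation table in the tracking database is the permitted alternative. No block size or other means of balance is stated for either method.

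The Analyses section compares outcomes "across study groups with analysis of covariance (ANCOVA) models (or non-parametric alternatives such as the Kruskal-Wallis test, when indicated), controlling for baseline values". CSI is not named there. It appears later in the same section, for Aim 3: first in plots and correlations, then in an interaction model ("A similar analysis will be conducted with the established cutpoint on CSI scale or 40 out of 100"). The section also says that the pilot will look at effect sizes and clinical relevance more than at p-values.

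The Background explains why CSI matters to the investigators: older adults "who have higher baseline pain sensitivity may respond better when PA is combined with CBT-P versus a PA program alone". That is a statement about response to treatment. It does not say that CSI predicts the outcome in every arm.

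**The concern.** The usual rule is to analyse by the factors used to randomise. A stratified design sets out to balance the arms on CSI. An analysis that ignores CSI leaves any variation due to it in the residual. What follows depends on two things the documents do not settle.

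- **Is CSI prognostic?** It must predict 12-week TUG or PROMIS-HAQ beyond the baseline value of that outcome. If not, nothing is lost by omitting it.
- **Are the arms balanced within strata?** If they are, the estimate is already protected from CSI imbalance, but the model does not know this and reports too large a standard error. If they are not, the standard error is right, but the estimate carries avoidable noise.

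The stake is the width or the quality of the pairwise comparisons. With about 20 patients per arm, the interval is an important part of judging whether a difference reaches clinical relevance.

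**Working it through.** **Inputs from the documents.** The sample size is 60 ("we are confident we can enroll n=60 older veterans with cLBP"), with equal allocation to three arms, so 20 per arm. There is one stratification factor with two levels. The model has arm and baseline as terms. The plan gives no power, SD or CSI–outcome association, so it has no figure of its own to reproduce.

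**Assumptions.** δ is the CSI effect in residual SDs, net of baseline and the same in every arm: 0, 0.2, 0.3, 0.5, 0.8 and 1.0. p is the share above 40: 50% or 30%. Follow-up is complete and tests are two-sided at 5%.

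**Formula.** Set the residual variance with CSI in the model to 1. Leaving CSI out adds δ²p(1−p).

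- Balanced strata: the arm contrast is free of CSI, so its true variance stays the same while the reported variance rises. The reported SE is too large by √(1 + δ²p(1−p)). At p = 0.5 and δ = 0.5 this is √(1 + 0.25 × 0.25) = √1.0625 = 1.031.
- Simple randomisation within strata: the true variance rises by about the same factor, so the reported SE is right and the loss is real.
- Partial R² is δ²p(1−p) / (1 + δ²p(1−p)); for δ = 0.5 it is 0.0625/1.0625 = 0.06.

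**Simulation.** There were 20,000 runs per scenario, with outcome = 0.7 × baseline + δ × stratum + standard normal error. One pairwise contrast was taken with and without the stratum term. The Monte Carlo error of a 5% rate is about 0.15 points.

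| δ | Partial R² (p = 0.5) | Formula SE ratio (p = 0.5) | Balanced: SE excess, p = 0.5 | Balanced: SE excess, p = 0.3 | Balanced: actual error rate, p = 0.5 | Simple: change in true SD when CSI is omitted, p = 0.5 |
|---|---|---|---|---|---|---|
| 0 | 0 | 1.000 | 0.0% | 0.0% | 5.0% | −1.0% |
| 0.2 | 0.01 | 1.005 | 0.5% | 0.4% | 4.9% | −0.5% |
| 0.3 | 0.02 | 1.011 | 1.2% | 1.0% | 4.9% | +0.5% |
| 0.5 | 0.06 | 1.031 | 3.2% | 2.7% | 4.1% | +2.1% |
| 0.8 | 0.14 | 1.077 | 8.0% | 6.8% | 3.4% | +6.8% |
| 1.0 | 0.20 | 1.118 | 12.4% | 10.5% | 2.8% | +10.4% |

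With balanced strata, the true SD of the estimate changes by at most 0.2%. With simple randomisation, the model SE without CSI is 0.99 to 1.00 times the true SD, and the error rate is 4.9% to 5.3%.

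**Second check under other assumptions.** This used 40% above 40, a baseline–outcome correlation of 0.6, permuted blocks of 6 within stratum, and 4,000 runs. Adding CSI multiplies the 95% interval width by 0.975, 0.946 and 0.892 at partial R² of 0.05, 0.10 and 0.20, against √(1 − R²) = 0.975, 0.949 and 0.894. In stated precision this equals 60 × (1/(1 − R²) − 1) = 3.2, 6.7 and 15 extra patients. At R² = 0.10 the true SE is 0.309 without CSI and 0.308 with it, while the model without CSI reports 0.318. Power for a difference of 0.8 SD goes from 69% to 73% at R² = 0.10, and from 72% to 80% at 0.20. With one large shuffled batch per stratum, which balances less well, the true SE itself differs: 0.319 without and 0.310 with at R² = 0.10, and 0.307 and 0.290 at 0.20. The pattern is the same with 51 patients analysed.

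**Cost of adding CSI when it predicts nothing.** Residual degrees of freedom go from 60 − 3 − 1 = 56 to 55, and the t multiplier from 2.0032 to 2.0040, a 0.04% wider interval under exact balance. The simulations put the cost at 0.1% with blocks of 6, 0.6% with one large batch and about 1% with simple randomisation.

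**The case against.** The strongest objection is that the documents argue for effect modification, whereas the table assumes a CSI effect common to all arms. If CSI changes the outcome only under PA + CBT-P, omitting it hardly matters. A simulation of that case (balanced strata, half above 40, 10,000 runs, PA + CBT-P versus PA) gives a model SE too large by only 0.1%, 0.3%, 0.8% and 1.3% for interactions of 0.3, 0.5, 0.8 and 1.0 SD. That is correct. The larger figures need a strong prognostic main effect that no part of the plan supports.

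It is also fair to say that the pilot is to be read by effect sizes, that these hardly move with balanced strata, and that any error in the SE is conservative. These points keep the matter small.

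Two other objections carry less weight. The Aim 3 models do contain CSI, but as an interaction with arm, so they do not supply the overall Aim 2 comparison. The term for baseline values might have been meant to include CSI, but the natural reading is each outcome's own baseline, and if more was intended the text should say so.

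**Conclusion.** The point holds as a modest improvement. The plan stratifies by CSI and does not carry the stratum into the Aim 2 model. There is no bias and no type I error inflation. For assumed prognostic effects up to 0.3 residual SD, the loss is about 1% or less. At 0.5 SD it is 2% to 3%, and at 1.0 SD it is 10% to 12%. With balanced strata the loss is in stated precision; with simple randomisation it is in the estimate itself. If CSI is not prognostic there is no loss. All CSI effects and stratum shares are assumptions, so the documents do not fix the actual size. The case for the change is that the possible gain is several percent and the possible cost is about 1% at most.

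**What to change.** Write the Aim 2 model, for primary and secondary outcomes, as follow-up value = arm + baseline value of that outcome + CSI stratum (>40 versus ≤40, as randomised). Report adjusted pairwise differences with 95% confidence intervals. State whether the envelope batches, or the database table, are blocked within stratum, since that decides which of the two effects applies.

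A separate small point arises in the same sentence of the plan: the Kruskal-Wallis test adjusts for neither baseline nor stratum. Where a non-parametric method is needed, a rank ANCOVA that keeps both would match the stated intention.

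The cost is one model term, one residual degree of freedom and one sentence on blocking. CSI is already collected before randomisation, so no new data are needed.

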Another novel aspect of this project will be the evaluation of baseline pain sensitivity, measured with field-based techniques, as a potential predictor of response to the interventions. Some patients with cLBP have a lower threshold for pain, due to an augmented central pain processing mechanism. As such, measures of pain sensitivity may prove useful in understanding an ongoing refractory pain-process; it is possible that patients who have a lower threshold for pain may respond differentially to behavioral interventions. In particular, these patients may experience greater improvement when CBT-P is offered as an additional program component (compared to PA alone), since these cognitive skills have been shown to influence pain processing. This pilot study will be an important step, ultimately leading to guidance regarding whether some older adults with cLBP should be offered a PA only vs. PA + CBT-P.

To our knowledge this will be the first study to examine the home-based PA only and PA + CBT-P programs among older adults with cLBP, as well as the first to evaluate central pain sensitivity as a predictor of response to these interventions. Therefore preliminary data are needed to support a larger project. Our specific aims are:

**Specific Aim 1:** Examine the feasibility of conducting 12-week home-based, telephone-supported programs of: 1.) PA only and 2.) Combined PA+CBT-P, among older veterans (65+ years) with cLBP. Quantitative measures of feasibility will include the proportions of patients who initiate and complete the programs and adherence to in-home PA recommendations and cognitive behavioral skills practice. We will also collect in-depth qualitative information to assess aspects of the interventions that may need to be modified prior to a larger study.

**Specific Aim 2:** Collect preliminary data to evaluate the efficacy of the PA only and PA + CBT-P programs among older veterans with cLBP. Main outcomes will be an objective test of general physical function (timed up-and-go (TUG)) and self-reported physical function (PROMIS Health Assessment Questionnaire (PROMIS-HAQ)). Secondary outcomes will include: Patient Specific Functional Scale (PSFS), Satisfaction with Physical Function Scale, LBP-specific disability (Roland-Morris Low Back Pain and Disability Questionnaire (R-MDQ)), and the Coping Strategies Questionnaire.

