## RESEARCH DESIGN AND METHODS

**Study Design:** This project will be a randomized controlled pilot trial of 12-week programs of PA only and PA + CBT-P, both supported by telephone, among 60 older adults with cLBP at the Durham VA Medical Center (VAMC). Participants will be randomly assigned with equal allocation to the two intervention groups or a wait-list control (WL) group. Participants will complete assessments at baseline, then approximately 12-weeks later. Participants in the WL group may choose to participate in the PA only or PA + CBT-P program following 12-week assessments. The 12-week follow-up was chosen because this is a reasonable time frame for older adults to experience neuromuscular adaptations and changes in general physical function. We chose a home-based exercise program because of its feasibility for widespread dissemination in the VA and because prior work has shown that home-based PA programs are safe and effective for improving physical function among older adults. We have chosen telephone-based approach because we expect this method of communication will be well received by older veterans, based on our prior and ongoing work in telephone-based PA support for osteoarthritis. We have chosen to include a control group in this pilot trial to account for any general improvement or changes in primary care intervention that may be observed in the course of cLBP. Participants will be paid \$30 for each assessment visit for time and travel.

**Participants and Recruitment:** The target sample for this study will include older veterans (65+ years) with cLBP at the Durham VAMC. We may over-sample women to ensure this important demographic group of Veterans is adequately represented in the study. In particular, we may prioritize contacting women Veterans who meet study entry criteria so that they comprise at least 30% of the study sample. We will have three recruitment mechanisms:

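### The pilot's observed effect sizes are made inputs to the larger trial's sample size, although 20 per arm estimates them too imprecisely to set a target difference

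*Combined protocol and SAP*

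**What the plan says.** The Study Design paragraph of Research Design and Methods sets a total of 60 participants: "Participants will be randomly assigned with equal allocation to the two intervention groups or a wait-list control (WL) group". That is 20 per arm. Specific Aim 2 names two primary outcomes: "Main outcomes will be an objective test of general physical function (timed up-and-go (TUG)) and self-reported physical function", the latter by PROMIS-HAQ.

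The Analyses paragraph in the same part of the document begins: "We will compare outcomes across study groups with analysis of covariance (ANCOVA) models", controlling for baseline. It concedes the limits of the sample: "Since this is a pilot study with small sample size, even clinically relevant differences may not be reflected as statistically significant differences". It continues: "Therefore we will focus on effect sizes for the two intervention groups and evaluation of whether between-group difference reflects a threshold of clinical relevance". The next sentence opens by referring back to those results. It adds baseline means and SDs and baseline/follow-up correlations to the list, and ends: "attrition rate will also be used to calculate the appropriate sample size for a larger clinical trial".

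The documents give no value for the relevance threshold, no target difference for the larger trial, no confidence interval for the effect sizes, and no rule for deciding whether to proceed.

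**The concern.** The SDs, correlations and attrition are listed as additions to whatever the sentence refers back to. The only available antecedent is the preceding sentence: the effect sizes and the check against a relevance threshold. So the observed effects are themselves inputs to the sizing, and nothing else in the plan could serve as the target difference.

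The required sample size varies with the inverse square of the target difference, so an error in the target is magnified. An estimate too high by a factor of 1.73 gives a trial one third of the right size; one too low by the same factor gives a trial three times too large. The paragraph itself says the sample is too small to show relevant differences reliably, and that imprecision carries straight into the sizing.

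At stake is the design of the later trial. It could be underpowered after a lucky pilot, or dropped as unaffordable after an unlucky one.

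**Working it through.** **From the documents.** 60/3 = 20 per arm; ANCOVA adjusted for baseline; two programmes against wait-list on two primary outcomes, so four primary comparisons. The plan gives no power calculation to reproduce.

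**Assumed, because the documents do not say.** No attrition; baseline/follow-up correlation r = 0.5, with 0 and 0.7 as the range; larger trial at 80% power and two-sided 0.05; SD and correlation known, which isolates the effect of the target difference; normal approximation; the observed effect used directly as the target.

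**Step 1: precision of the pilot estimate.** SE = √(2(1 − r²)/n), in SD units.
- r = 0.5: √(2 × 0.75/20) = 0.274
- r = 0: √(2/20) = 0.316
- r = 0.7: √(2 × 0.51/20) = 0.226

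**Step 2: calculated size.** N per arm = 2(1 − r²)(1.960 + 0.842)²/d². At r = 0.5 this is 2 × 0.75 × 7.849/d² = 11.77/d². For a true effect of 0.5 SD the correct size is 11.77/0.25 = 47 per arm.

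**Step 3: spread when the true effect is 0.5 SD, r = 0.5.** The quartiles of the observed effect are 0.5 ± 0.6745 × 0.274, that is 0.315 and 0.685. They give 11.77/0.315² ≈ 118 and 11.77/0.685² ≈ 25 per arm.

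**Step 4: three-fold errors.** N is at least three times too small when the observed effect exceeds 0.5 × √3 = 0.866: z = 0.366/0.274 = 1.34, probability 9%. It is at least three times too large, or the estimate has the wrong sign, when the observed effect is below 0.5/√3 = 0.289: z = −0.211/0.274 = −0.77, probability 22%, of which 3% is wrong sign. The same steps elsewhere, sizes rounded to the nearest whole number:

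| True effect (SD) | r | Correct N per arm | At least 3-fold too small | At least 3-fold too large, or wrong sign |
|---|---|---|---|---|
| 0.3 | 0.5 | 131 | 21% | 32% |
| 0.5 | 0 | 63 | 12% | 25% |
| 0.5 | 0.5 | 47 | 9% | 22% |
| 0.5 | 0.7 | 32 | 5% | 17% |
| 0.8 | 0.5 | 18 | 2% | 11% |

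**Step 5: true power of the larger trial.** Power = Φ(2.80 × d_true/d_obs − 1.96). It is below 50% when d_obs exceeds 0.5 × 2.80/1.96 = 0.715: z = 0.215/0.274 = 0.78, probability 21.6%. Dividing by the 96.6% of pilots with a favourable estimate gives 22% (26% at r = 0, 17% at r = 0.7).

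**Step 6: no true effect.** A calculated size of 200 per arm or fewer (an illustrative cut-off, not the plan's) needs d_obs of at least √(11.77/200) = 0.243: z = 0.243/0.274 = 0.89, probability 19% for a single comparison. This does not depend on r, which cancels. For at least one of the four primary comparisons, simulation of 400,000 pilots with a shared control arm and an assumed outcome correlation of 0.4 gives 46% (50% at correlation 0, 41% at 0.7).

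**Step 7: the alternative.** With the target fixed in advance, the pilot contributes an estimated variance on about 60 − 3 = 57 degrees of freedom. The 2.5% and 97.5% points of χ²₅₇/57 are 0.67 and 1.40, so the planned size stays within 0.67 to 1.40 times the correct one in 95% of pilots, taking the variance as the only uncertain input.

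**The case against.** The strongest reply is that the plan contains no sizing formula. It says the results will be used, not that the raw point estimate will be the target, and the sentence referred to also mentions a relevance threshold. If that threshold were given a value and made the target, most of the problem would go. This stands in part: the formula in Step 2 is a reconstruction, and the figures are conditional on it. But the threshold has no value and is not tied to the sizing, while the effect sizes are among the stated inputs.

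Some stronger readings are not supported:
- A reader might infer that a programme with no effect would give the sponsor something to plan on at least half the time. That counts every estimate above zero. An observed 0.1 SD implies 11.77/0.01 ≈ 1,177 per arm, which few would plan on. For one comparison the chance of 200 per arm or fewer is 19%, and of an estimate above 0.5 SD it is 3% (6% at r = 0). Nothing says the best of four comparisons would be chosen, so 46% is an upper illustration.
- A reader might infer that sizing the next trial is the pilot's purpose. The three aims are feasibility, preliminary efficacy and predictors of response. Specific Aims says only: "Therefore preliminary data are needed to support a larger project". Sizing is an additional use.
- A reader might infer that attrition worsens every figure. At 17 per arm the SE rises to √(1.5/17) = 0.297, but the 50% chance of a favourable sign under no effect does not change.
- A reader might infer that only lucky results will be taken forward. The documents contain no budget, cut-off or go/no-go rule.

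It is also true that the harm is downstream, and that the later trial's own protocol could still set a proper target.

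**Conclusion.** The point holds in limited form. The plan lists an imprecise observed effect among the inputs to a later sample size and offers no other target. If that effect is used as the target, a moderate true effect of 0.5 SD leads to a three-fold or larger error in about 31% of pilots at r = 0.5 (9% + 22%), more often towards too large. The risk is greater for a small true effect (53% at 0.3 SD) and modest for a large one (about 12% at 0.8 SD). True effect, correlation, power and absence of attrition are all assumptions.

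Using the pilot's SDs, correlations and attrition for planning is sound and is not criticised. No participant, estimate or conclusion of this trial is affected. I rate it a cheap improvement.

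**What to change.** In the Analyses paragraph:
- Remove the observed effect sizes from the inputs to the larger trial's sample size.
- State that its target difference will be the clinically relevant difference for TUG and for PROMIS-HAQ, with values fixed before the pilot data are seen.
- Keep the pilot as the source for variability, baseline/follow-up correlation and attrition.
- Report the between-group estimates with 95% confidence intervals, and use them only to check whether the fixed target is compatible with the data.

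The cost is a few sentences and agreement on two values, with no extra data, visits or participants. The small downside is that the larger trial may come out bigger than one sized on a favourable pilot estimate.

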**Specific Aim 3:** Examine whether baseline distal Pressure-Pain Threshold, an established biological marker of pain sensitization, and the Central Sensitivity Inventory, which measures health-related symptoms common to central pain sensitization, predict differential response to the PA only and / or PA + CBT-P programs among older veterans with cLBP.

There is a need to develop and disseminate effective programs to improve PA and ultimately physical function in this patient subgroup. This project will be a key first step in evaluating a home-based PA and PA + CBT-P programs that could be widely disseminated in the VA at relatively low cost and reach many functionally vulnerable older veterans with cLBP.

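### The first Aim 3 step sets pain sensitivity against raw change in the two active arms only, so it can compare the programmes with each other but cannot show response to either against no programme

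*Combined protocol and SAP*

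**What the plan says.** Aim 3, in Specific Aims, asks whether baseline pressure-pain threshold (PPT) and the central sensitivity inventory (CSI) "predict differential response to the PA only and / or PA + CBT-P programs".

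The Analyses paragraph of Research Design and Methods takes this in two steps.

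- **Step 1:** "we will first plot baseline PPT and CSI values vs. changes in outcomes for each intervention group; we will also calculate correlations". The stated use is to see whether these associations "may differ between the two intervention groups". The wait-list arm is not mentioned, and nothing is said about adjusting change for the baseline outcome.
- **Step 2:** a study group by dichotomised PPT term (cut at 4 kg) is added to the ANCOVA models, with a similar analysis for CSI at 40. Those models compare the study groups and control for baseline values.

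On the design, the Study Design paragraph says: "Participants will be randomly assigned with equal allocation to the two intervention groups or a wait-list control (WL) group". The total is 60. On the reason for a control arm it says: "We have chosen to include a control group in this pilot trial to account for any general improvement or changes in primary care intervention".

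**The concern.** A correlation between a baseline marker and raw change inside one treated arm mixes three things: prediction of response to treatment, ordinary prognosis, and regression to the mean. The wait-list arm is the trial's means of separating the first from the other two, and Step 1 leaves it out.

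This matters because Aim 3 is wider than PA versus PA + CBT-P. Its and/or phrasing also covers response to each programme taken alone, and response to PA only has meaning only against no programme. A reader who sees a clear slope in the PA plot could conclude that sensitive patients respond to PA, when untreated participants might show the same slope. Specific Aims presents the pilot as a step towards guidance on who should be offered which programme, so such a misreading could carry forward.

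**Working it through.** The plan gives no figure to reproduce: Aim 3 has no power or precision statement.

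**Inputs.** From the documents: 60 participants in three equal arms, so 60/3 = 20 per arm. Assumed, because the documents do not give them: rho0 and rho1, the correlations of sensitivity X with the baseline and 12-week outcome, and r, the correlation between baseline and 12-week outcome. X is scored so that higher means more sensitive (the sign reverses for PPT itself), and the outcome so that higher means worse. A negative correlation then looks like more improvement in sensitive patients.

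**1. Correlation with raw change.** With equal SDs at both visits,

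corr(X, Y1 - Y0) = (rho1 - rho0) / sqrt(2(1 - r)).

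A treatment effect that is the same for everyone in an arm does not alter this. Three cases, all without effect modification:

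- *X linked to follow-up only through the baseline score* (rho1 = r × rho0). The formula becomes -rho0 × sqrt((1 - r)/2).
  - rho0 = 0.3, r = 0.7: -0.3 × sqrt(0.15) = -0.116
  - rho0 = 0.4, r = 0.7: -0.4 × sqrt(0.15) = -0.155
  - rho0 = 0.5, r = 0.6: -0.5 × sqrt(0.20) = -0.224
- *X linked only to stable function* (rho1 = rho0): 0.
- *X related to natural course* (rho1 - rho0 between ±0.1 and ±0.2, r from 0.5 to 0.8): ±0.10 to ±0.32, in either direction.

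**2. Precision at 20 per arm.**

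- One correlation near zero: 95% half-width tanh(1.96/sqrt(17)) = 0.44.
- Difference between two arms, Fisher z scale: 1.96 × sqrt(2/17) = 0.67. The smallest difference detectable with 80% power at two-sided 5% is (1.96 + 0.84) × sqrt(2/17) = 0.96.

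**3. Simulation.** 6,000 runs per scenario, 20 per arm, a common effect of 0.5 SD in both active arms, no effect modification, X split at its mean for the interaction model. Share of runs significant at 5%:

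| Scenario (rho0, rho1, r) | One active arm | At least one of two | Difference between active arms | Three-arm ANCOVA interaction |
|---|---|---|---|---|
| Through baseline only (0.4, 0.24, 0.6) | 11.5% | 22.1% | 4.4% | 5.5% |
| Through baseline only (0.5, 0.25, 0.5) | 19.6% | 34.8% | 4.8% | 4.6% |
| Through baseline only (0.6, 0.30, 0.5) | 25.0% | 43.7% | 4.7% | 4.8% |
| Natural course (0.4, 0.6, 0.6) | 15.9% | 28.3% | 5.0% | 4.8% |
| Natural course (0.3, 0.5, 0.7) | 19.1% | 35.4% | 5.4% | 5.1% |
| Stable function only (0.4, 0.4, 0.6) | 4.9% | 9.2% | 4.6% | 5.2% |
| No relation (0, 0, 0.6) | 4.8% | 9.8% | 5.0% | 5.0% |

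The single-arm correlation can mislead. The contrast of the two active arms and the planned interaction model both hold their nominal level.

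**The case against.** The case for leaving the plan alone is substantial, and most of it stands.

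- **Purpose of the step.** It is there to compare the two randomised active arms, which matches the stated hypothesis that sensitive patients gain more when CBT-P is added. Regression to the mean and natural course do not bias that contrast. This stands. It leaves open only the comparison of each programme with none.
- **The next step.** The interaction model adjusts for baseline and, since it compares the study groups, takes in wait-list. This also stands and limits the harm. What it leaves is coarse: PPT and CSI enter only as two categories.
- **No test is planned.** The correlations are to be calculated, and the pilot says it will focus on effect sizes. The rejection rates above therefore describe how often a single-arm correlation would look noteworthy, not the error rate of a planned test.
- **Size.** An artefact of -0.12 to -0.22 is at most about half the single-arm half-width of 0.44.

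Two stronger readings are tempting. A reader might infer that regression to the mean must distort Step 1. The documents do not support this: the predictor is PPT or CSI, not the baseline outcome, so the artefact needs a link with the transient part of the baseline score. That is plausible but undocumented. A reader might also infer that the plots will carry the Aim 3 conclusion because the interaction test is unlikely to reach significance. That is a forecast about reporting; nothing in the Analyses paragraph ranks the plots above the model.

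**Conclusion.** Minor. Step 1 is sound for its stated use, PA against PA + CBT-P. On its own it cannot address whether sensitivity predicts response to either programme against no programme. Step 2 does address that, but only through cut-points, so the continuous association is never seen in the wait-list arm.

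The size of the possible artefact depends on assumptions about structure as well as magnitude. It is about -0.12 to -0.22 if sensitivity reaches follow-up only through the baseline score (rho0 0.3 to 0.5, r 0.6 to 0.7), zero if sensitivity reflects stable function only, and of either sign if sensitivity is related to natural course. The documents do not say which case applies. The finding does not extend to Aim 3 as a whole: the planned interaction analysis is not undermined.

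**What to change.** Amend the Aim 3 text in the Analyses paragraph:

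1. Include the wait-list arm in the plots and associations.
2. Replace raw change with the 12-week outcome adjusted for its baseline value.
3. Add study group by continuous PPT and study group by continuous CSI terms to the ANCOVA, alongside the planned dichotomised ones.
4. Report the slope differences (each active arm versus wait-list, and PA + CBT-P versus PA) with 95% confidence intervals.
5. State that within-arm correlations are descriptive and are not evidence of treatment response.

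The cost is wording and a little analysis time, since all the data are already to be collected. There is a small downside: 2 predictors × 3 contrasts = 6 slope differences per outcome, or 12 over the two primary outcomes. These will be imprecise at about 20 per arm and add multiplicity, so they should be labelled exploratory.
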